## 4 STUDY DESIGN

### 4.1 OVERALL DESIGN

#### Aims/Hypotheses:

*Note: Aim 1 of the grant is to be performed in ANIMAL subjects only. However, Aim 2 of the grant is to be carried out in human subjects and therefore the design of Aim 2 is somewhat dependent on the results of Aim 1. For information purposes only, both are described below:*

**Specific Aim 1: Determine precise parameters/dosages for modulating multisensory plasticity in fusiform cells (FCs) and cartwheel cells (CWCs) in normal and pathological (tinnitus) circuitry in guinea pigs. Hypothesis 1: Presenting bimodal AN-SS stimuli with optimal parameters to guinea pigs with tinnitus will reverse pathological StDP in FCs and CWCs.**

**Specific Aim 2: Test parameters/dosages determined in Specific Aim 1, for modulation of multisensory plasticity in human subjects with changes in tinnitus severity as the outcome measure.** Hypothesis 2: AN-SS stimuli with optimal dosage/parameters (based on the results of Specific Aim 1), will effectively modulate DCN circuitry to reduce tinnitus in humans.

Experiment 2a: Using a double-blind cross-over model, we will use a bimodal AN-SS paradigm with optimal stimulus parameters based on the results of Specific Aim 1 to assess changes in subjects' tinnitus perception. Modulations in tinnitus perception will be assessed using objective loudness matching and subjective measures (standard questionnaires) in response to active and sham bimodal stimuli. Neural circuitry changes will be assessed by examining changes in the severity of subjects' tinnitus. It is anticipated that chosen bimodal intervals and durations of treatment (dose) will reduce the abnormal percepts. Experiment 2b: Subjects will

be monitored during a washout period for a return to baseline to determine durability of effect. To assess dose-response of the bimodal modulation, the length of bimodal stimulation treatment will be varied and effects and duration of effect on tinnitus will be assessed as above

**Phase:** Phase I/II

**Type of design:** Double-blinded, cross-over design. There will be two treatment arms (treatment and sham). All subjects will participate in both arms of the study. This is a single-site study. Total duration of the study for each subject will be 36 weeks.

## 4.2 SCIENTIFIC RATIONALE FOR STUDY DESIGN

Previous studies examining efficacy of various tinnitus treatments have shown a strong placebo effect (Dobie 1999). Therefore, is important to include a placebo arm in order to truly evaluate the efficacy of the device and treatment. It is also important that both the subject and the administrator (all study team members) are also blinded to the enrollment and assignment of the subjects for the same reasons. The placebo stimulus is an auditory stimulus which is benign and shown in the first trial to have no effect (Marks et al, Science Translational Medicine, January, 2018, HUM00088432).

## 4.3 JUSTIFICATION FOR DOSE

The justification for dosage is based on Aim 1 of the project (preclinical experiments) as stated above.

## 4.4 END OF STUDY DEFINITION

A participant is considered to have completed the study if he or she has completed all phases of the study including the last visit or the last scheduled procedure shown in the Schedule of Activities (SoA), Section 1.3.

## 5 STUDY POPULATION

### 5.1 INCLUSION CRITERIA

In order to be eligible to participate in this study, an individual must meet all of the following criteria:

1. Must be 18 years of age or older.

2. A score of >17 points on the Tinnitus Functional Index, as measured at the screening visit.
3. Must report constant, subjective, preferably unilateral tinnitus without any active external or middle ear pathology.
4. No greater than a moderate hearing loss at the tinnitus frequencies ( $\leq 55$  dB HL) and no greater than moderate hearing loss ( $\leq 50$  dB HL) from 125 – 6000 Hz .
5. Must be able to modulate their tinnitus with a somatic maneuver
6. Preferably onset of tinnitus less than one year ago, but for at least 6 months. Tinnitus should be bothersome.
7. Absence of retrocochlear pathology/ VIIIth nerve lesion
8. No participation in a tinnitus treatment regimen within the past six months and no participation in Stage 1 trial.
9. Resides within 100 miles of study site.

## 5.2 EXCLUSION CRITERIA

An individual who meets any of the following criteria will be excluded from participation in this study:

1. Anyone not meeting the above inclusion criteria, and in addition:
2. Diagnosis of Meniere's disease
3. Diagnosis of Semicircular Canal Dehiscence.
4. Unilateral or bilateral cochlear implant recipients
5. Diagnosis of acoustic neuroma
6. Evidence of retrocochlear disease
7. Patients with any indwelling electronic stimulation devices
8. Current or previous use of any acoustic hearing aid or over-the-counter personal sound amplification product (PSAP) in the last 6 months.
9. Current or former use of any of the following medications within the past 6 months: high dose aspirin ( $>325$ mg/day), high dose NSAIDs (ibuprofen, Motrin, Celebrex) ( $>800$ mg/day), narcotics (any opioids), lithium, clonazepam, oxazepam, cholinergic medications (anti-dementia medications), anti-depressant medications (serotonin specific reuptake

inhibitors; SSRIs, tri-cyclic anti-depressants; TCAs); anti seizure/convulsant medications (Depakote), anti-psychotic medications (Haldol, Seroquel), Ototoxic medications, other chemotherapy agents, central nervous system stimulants, and benzodiazepines.

10. Current diagnoses of any of the following: obsessive compulsive disorder (OCD), schizophrenia, bipolar disorder, extreme generalized anxiety disorder, drug/alcohol dependence.
11. Pregnant or Nursing.

### 5.3 LIFESTYLE CONSIDERATIONS

During this study, participants are asked to:

- Refrain from participation in any other tinnitus treatment
- Report any changes in health status
- Report any changes in prescribed or over-the-counter medications

### 5.4 SCREEN FAILURES

Screen failures are defined as participants who consent to participate in the clinical trial but are not subsequently randomly assigned to the study intervention or entered in the study. A minimal set of screen failure information is required to ensure transparent reporting of screen failure participants, to meet the Consolidated Standards of Reporting Trials (CONSORT) publishing requirements and to respond to queries from regulatory authorities. Minimal information includes demography, screen failure details, eligibility criteria, and any serious adverse event (SAE).

Individuals who do not meet the criteria for participation in this trial (screen failure) because of a recent participation on another tinnitus treatment regimen may be rescreened once the observed period of time as passed as stated in the protocol. **Rescreened participants should be assigned the same participant number as for the initial screening.**

### 5.5 STRATEGIES FOR RECRUITMENT AND RETENTION

#### **General procedures:**

Study team members will recruit patients from patient populations seen in the otology and audiology clinics at UMHS, as well as those who have contacted [name] or other study team members to report having tinnitus. Once they have contacted a study team member, they will receive an automatic reply which will be sent using the Mail Chimp email automation platform. Please see additional documentation for Mail Chimp platform security information (Attachment A) and an email script (Attachment B) that will be sent to potential participants. Within the email script, potential participants will be directed to the clinical study website which will appear on the umhealthresearch.org website. Participants will be asked to create an account

and log in, and then they will have the ability to contact the study team through the website if they are interested in participating. Please see Attachment C for content that will be posted on umhealthresearch.org. Once a potential participant has contacted the study team using the umhealthresearch.org website, he/she will be contacted by a member of the study team via phone, email, or secure messaging via the umhealthresearch.org website in order to confirm that they meet the inclusion and exclusion criteria. Please see additional documentation for phone and/or email script (Attachment D). Once such information is confirmed, they will be scheduled for an initial visit to the lab at which time consenting and candidacy evaluations will be performed.

Subjects may also sign the informed consent through the SignNow application. Subjects will meet with a staff member through HIPAA compliant Zoom videocall platform where the staff member will review the informed consent with the subject and answer any questions the subject may have prior to signing the document.

The patient will have the opportunity to ask questions at all times throughout the recruitment process. All questions or concerns will be addressed by a study team member. Through purposeful sampling, we will attempt to include a diverse set of respondents based on ethnic, socioeconomic, and educational backgrounds.

Target study sample size: We will enroll 400 subjects in order to assign up to 100 subjects to 2 treatment arms. We anticipate testing 34 subjects per year in order to meet this recruitment goal. There is one recruiting site (University of Michigan).

Subjects will be provided compensation for parking at each visit.

## 6 STUDY INTERVENTION

### 6.1 STUDY INTERVENTION(S) ADMINISTRATION

[figure not shown]
#### 6.1.1 STUDY INTERVENTION DESCRIPTION

*Describe the study intervention(s) and control product. Product information can usually be obtained from the:*

[figure not shown]
[figure not shown]
- The investigational devices for providing the stimulation protocols have been designed by members of the [name] Lab and fabricated by In2being, LLC. The device provides acoustic and electrical stimulation at levels deemed safe by OSHA, ISO and ANSI.
- The device is labeled “for investigational use only”
- Final labeling for a marketed device will be obtained after FDA final review after completion of the trial. In2being, LLC will incorporate any changes to the labeling that are suggested.
- A pre-submission has been reviewed already by the FDA and they were in agreement that this device would be de novo, non-significant risk.

*In addition:*

- FDA and the IRB consider our device class 2 de novo, thus we do not require an IDE to run the clinical trial, stage 2.
- The study intervention is not yet commercially available. Since the stage 1 clinical trial that has been completed, we are hiring In2being to upgrade the devices so that the next generation is FDA compliant.
- *If conducting a study with a device, the following information should be included:*
  - Device size(s): Less than 3"/2"/7"
  - Device model(s): Gen 2
  - Description of each component:
    - CPU
    - SD card for data storage
    - power supply
    - rechargeable lithium ion batteries
    - electrical stimulator
    - sound stimulator
    - earphones
    - stimulating pads
  - Device settings and programming:
    - See Figure 1 for all device tunable parameters
    - Auditory SPL below 95 dB SLP
    - Current less than 3 mA (see Figure 1)
    - Misapplication of electrodes is detected by the device as shown by red light.
    - Device has only two settings (on/off), limiting subject errors.
  - Duration of stimulation (30-60 min/day).
  - Once per day
  - Current levels with known potentiometer values and Maximum SPL are shown in Fig. 2
- **Figure 1: Device Tunable Parameters.** Each indicated parameter is regulated by the device. Current level, audio intensity and frequency content are altered on an individualized basis for the treatment; all other parameters remain fixed.
-

- **Figure 2. Calibration Data.** Stimuli are calibrated prior to device use. **A)** Each device features an internal self-calibration for the electrical stimulator. This check is run every trial to ensure appropriate treatment stimulation. This feature also checks for open and short circuits, which indicate improper electrode placement. For a given potentiometer value (x-axis), the device output current (right y-axis) and regulated voltage (left y-axis) are shown. **B)** Device ear phones are matched to a device and calibrated using a standard microphone. Dashed line shows earphone output without limiter installed, solid with limiter.
- 
- 
- 

### 6.1.2 DOSING AND ADMINISTRATION

Each subject will have their tinnitus spectrum assessed with the Tinn Tester protocol (L. Roberts et al, 2008). This spectrum is digitized and programmed into the device as the signal to be delivered to the subject. The amplitude is limited to 95 dB SPL and is delivered together with an electrical stimulus delivered a short time after the auditory stimulus (as determined by the preclinical studies). This stimulus is presented by the device when the subject turns on the device. The device limits the time of presentation to 30-60 min per day.

This protocol is presented once a day for 30-60 minutes for 6 weeks. After that there is a washout period of 6 weeks in which no device is used. Subjects are tested once a week to assess the primary and secondary outcomes and when baseline is achieved. The second arm of the study begins for another 6 weeks. A second washout of 6 weeks occurs, end of study visit, and 12 weeks of follow up, after which the subject participation is ended. Completion of Arm 1 and Arm 2 do not necessarily have to be consecutive, and we will allow for 12 weeks in between in order to provide more flexibility for subjects. The dose will not change over the course of the study. Maximum duration of enrollment is 36 weeks.

The subjects will be trained on how to use the devices and place the earphones and electrode pads. Once they have been effectively trained, subjects will take the devices home to use for the 30-60 min/day periods. Once a week the primary and secondary outcomes will be tested along with any review or questions that the subjects need to be answered. Subjects are asked to use the device at the same time every day but If subjects miss a treatment they are instructed to use it at another time rather than miss that treatment.

## 6.2 PREPARATION/HANDLING/STORAGE/ACCOUNTABILITY

### 6.2.1 ACQUISITION AND ACCOUNTABILITY

In2being will provide a unique identifier for each device. The study team members will program the devices based on individuals' audiograms and tinnitus spectra and will show the subjects how to use the devices to implement the treatments. Devices will be returned to study team members following subject participation. Devices will be reprogrammed for subsequent subjects.

### 6.2.2 FORMULATION, APPEARANCE, PACKAGING, AND LABELING

See Figure 3.

**Figure 3. Generation 1 Device Pictures.** Generation 2 devices, to be tested in this study, will not be larger than the current designs, and will feature upgrades to ensure FDA approval.

Device dimensions: less than 2" x 5 " x 8"

#### 6.2.3 PRODUCT STORAGE AND STABILITY

Kept at room temperature when not in use. Subjects will be supplied with sufficient electrode pads and gel and earphone tips to ensure use of new pads and closed acoustic system with each treatment.

#### 6.2.4 PREPARATION

Subjects are required to gently wipe area for electrode contact (neck skin or face skin) with alcohol-based wipes prior to electrode placement.

### 6.3 MEASURES TO MINIMIZE BIAS: RANDOMIZATION AND BLINDING

Subjects are randomly assigned to group 1 (active first, then sham) or group 2 (sham first, then active) using Matlab's *randsample* command with a predetermined, fixed, secret seed value. *Randsample* generates random numbers using the Mersenne twister algorithm. We will enroll subjects in a 1:1 ratio to create a balanced study design. To ensure blinding, group assignment is generated *in silico* and assignment programmed into each device, without the intervention of a study member. This parameter is not made accessible to study members without password authorization. Devices are encrypted to prevent study team members or subjects from accessing device data in an unauthorized manner.

As the randomization list is generated algorithmically, the code can be reproduced with knowledge of the secret seed value. Unblinding may occur at the end of the study or in the case of an SAE related to the study (worsening of tinnitus, worsening of hearing threshold). Study investigators that do not have contact with subjects may unblind. Intentional and unintentional unblinding must be reported to the principle investigator.

Imperfect blinding could arise from the presence of the electrical stimulation present during active treatment. To avoid unblinding, subjects will be told that they may or may not feel electrical stimulation during both phases of the study. The previous study suggested that subjects tend to acclimate to the presence or lack of electrical stimulation during a day's treatment. Subjects will be discouraged from divulging whether they can feel the electrical stimulus.

No investigators are allowed to remain unblinded for the duration of the study. All analyses that could require unblinding (SAEs, worsening of a subject's tinnitus/hearing) will be identified by software, and the investigators notified by automated communication methods.

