## 8.2 SAFETY AND OTHER ASSESSMENTS

Subject participation will entail weekly visits to the lab for detailed assessments. The weekly visits to the lab will ensure that subjects are using the devices correctly and safely. The weekly visits also allow us to monitor changes in the tinnitus percept in response to device use or washout from the treatment. The regular assessments also provide us with the opportunity to detect any adverse events as soon as possible, should any occur.

Currently, there is no standard treatment for tinnitus that has been shown to be broadly effective at treating tinnitus, so participation in the study will not interfere with standard clinical intervention. Subjects will be informed during the consenting process that there are alternative methods of treatment such as sound therapy that they may find beneficial, and

referred to their primary care physician for referrals should they elect to pursue that form of treatment.

Regular assessments will also allow for swift intervention should a subject experience an adverse event or worsening of symptoms. We will stop the study should 10% of subjects show a persistent worsening in their symptoms. A subject's participation in the study will be discontinued following **both** 1) an increase of 16 or more points in TFI, **and** 2) an average increase of 12 dB in TinnTester compared to baseline, for two consecutive weekly measures. Both measures are our primary outcome measures. Using both criteria for determining discontinuation is critical as the tinntester measures tinnitus loudness, which reflects the circuitry changes identified in our preclinical studies. TFI is also important for the human study as it gauges the subject's subjective response to their tinnitus. However, TFI can also reflect outside life stressors unrelated to the treatment and could result in a subject's discontinuation for reasons unrelated to the treatment. A subject's participation can also be discontinued even if the criteria above is not met, but the subject feels their tinnitus is worse.

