any of the subjective or objective measures, and he/she wishes to discontinue participation in the study then he/she will withdraw from the study.

The study protocol and treatment device includes transmission of both acoustic and electric (transdermal) stimulation. For both stimulation types, stimuli are strictly controlled as to not cause harm or discomfort for the subject. For acoustic stimulation, the intensity is set at 30 dB SL (as determined by the subject's pure tone average), with each sound presented for 10 ms with 2 ms linear rise and fall times. This intensity level is expected to be within a comfortable listening range for each subject (based on clinical experience and previous research trial data). For the electric stimulation, the electrodes are positioned on the cheek overlying the trigeminal ganglion, the juncture of the temporomandibular joint or on the neck at overlying cervical nerves, C1 or C2, depending on which region modulates the tinnitus (based on the modulation maneuver checklist). Electrical stimulation levels are just below the threshold of muscular contraction (1-3 mA) as in the animal studies, limited by subject's comfort. This level of electric stimulation is typically one that initially results in a small, comfortable tingling at the stimulation site upon initial activation. However, based on our previous research trial subjects often report that electric stimulation cannot be detected within a few minutes of initial stimulation. This low level of electrical stimulation causes no harm to the subject. The sham protocol uses the same electrical and acoustic levels but the bimodal interval is wider than that used to induce STDP (>100 ms). Based on work in the animal, we expect that using wider bimodal intervals will cause no harm to the subject.

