#### 8.3.4 TIME PERIOD AND FREQUENCY FOR EVENT ASSESSMENT AND FOLLOW-UP

The occurrence of an adverse event (AE) or serious adverse event (SAE) may come to the attention of study personnel during study visits and interviews of a study participant presenting for medical care, or upon review by a study monitor.

All AEs including local and systemic reactions not meeting the criteria for SAEs will be captured on the appropriate case report form (CRF). Information to be collected includes event description, time of onset, clinician's assessment of severity, relationship to study product (assessed only by those with the training and authority to make a diagnosis), and time of resolution/stabilization of the event. All AEs occurring while on study must be documented appropriately regardless of relationship. All AEs will be followed to adequate resolution.

Any medical condition that is present at the time that the participant is screened will be considered as baseline and not reported as an AE. However, if the study participant's condition deteriorates at any time during the study, it will be recorded as an AE.

Changes in the severity of an AE will be documented to allow an assessment of the duration of the event at each level of severity to be performed. AEs characterized as intermittent require documentation of onset and duration of each episode.

The PI and ISM will record all reportable events with start dates occurring any time after informed consent is obtained until 7 (for non-serious AEs) or 30 days (for SAEs) after the last day of study participation. At each study visit, the investigator will inquire about the occurrence of AE/SAEs since the last visit. Events will be followed for outcome information until resolution or stabilization.

---

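### The Section 6.3 instruction not to divulge stimulus sensation carries no exemption for discomfort or adverse events, and the plan collects no systematic data on whether the blind held

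*Combined protocol and SAP*

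**What the plan says.** Section 6.3 raises the problem itself: "Imperfect blinding could arise from the presence of the electrical stimulation present during active treatment". Two measures follow. First, "subjects will be told that they may or may not feel electrical stimulation during both phases of the study". Second, "Subjects will be discouraged from divulging whether they can feel the electrical stimulus". As reassurance, the section offers an impression from the first-stage trial that subjects get used to the stimulus, or to its absence, within a day's session. On breaches it says: "Intentional and unintentional unblinding must be reported to the principle investigator".

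Other sections rely on what subjects report. Section 8.3.4 has "At each study visit, the investigator will inquire about the occurrence of AE/SAEs since the last visit" and "All AEs occurring while on study must be documented appropriately regardless of relationship". Section 8.2 says "The weekly visits to the lab will ensure that subjects are using the devices correctly and safely". It also says "Electrical stimulation levels are just below the threshold of muscular contraction (1-3 mA) as in the animal studies", with the subject's comfort as a further limit. Section 5.3 asks subjects to report changes in health status.

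The synopsis (Section 1.1) expects a slight tingling when the current starts, usually gone within minutes. It also says that subjects will know they receive both active and sham, but not which one they are on.

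The schedule of activities (Section 1.3), the assessments (Sections 8.1 and 8.2) and the statistical section (Section 9) contain no treatment guess, no sensation item and no analysis of blinding.

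**The concern.** There are two separate gaps.

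The first concerns safety reporting. The 6.3 sentence does not name the people it applies to and does not say where expected sensation ends and a reportable effect begins. A subject asked not to say whether the stimulus can be felt may reasonably hesitate to say that it stings. Effects at the electrode site are the most direct local effects of this device, and discomfort there is the sign that a comfort-limited level needs attention. If sensation differs between arms, any under-reporting could differ between arms too.

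The second concerns interpretation. Section 4.2 justifies the sham by a strong placebo effect in earlier tinnitus trials. Tinnitus loudness is adjusted by the subject, and the TFI and THI are questionnaires. In a crossover each subject can compare the two conditions during the second period. With no record of what subjects felt or believed, the final report can neither show that the blind held nor describe how far it failed.

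**Working it through.** No planned figure rests on this point, so the check is mainly a comparison of passages.

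1. **Scope of the instruction.** The 6.3 sentence concerns whether the stimulus is felt. It names no recipient and has no exception.

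2. **What depends on the same information.** Section 8.3.4 asks about adverse events at each visit, but the answers come from subjects under the 6.3 instruction. Section 8.2 uses weekly visits to check safe use and limits the current by comfort. The device log in Section 6.4 records daily use, open circuits and failures. It does not record discomfort, so it cannot replace the subject's report.

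3. **Evidence on the blind.** The only related provision is the duty in 6.3 to report unblinding events. That captures known breaches. It does not capture what each subject perceives or believes. Getting used to the stimulus within a session does not remove the tingling at its start, which may recur at each daily session.

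4. **How much sensation reveals.** This turns on the sham, which is described in incompatible ways:
   - Section 8.2: the same electrical and acoustic levels as active, with a wider interval (more than 100 ms).
   - Section 4.2: an auditory stimulus.
   - Section 6.3: electrical stimulation is treated as a feature of active treatment, and subjects are said to get used to having it or lacking it.

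   Under the 8.2 description, feeling the stimulus says little about the arm. Under the 4.2 description, it is nearly decisive.

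5. **Illustration of size.** Suppose a share p of subjects identify the treatment correctly in each arm, and believing oneself on active rather than sham changes the TFI by e points. The share believing active is p in the active arm and 1 − p in the sham arm. The false difference is then [p − (1 − p)] × e = (2p − 1) × e. Neither p nor e is in the documents; e = 5 to 10 is an assumption.

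| p | 2p − 1 | e = 5 | e = 10 |
|---|---|---|---|
| 0.5 | 0 | 0 | 0 |
| 0.6 | 0.2 | 1 | 2 |
| 0.7 | 0.4 | 2 | 4 |
| 0.8 | 0.6 | 3 | 6 |

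Section 3.1 takes a 13-point TFI reduction as clinically significant, so the largest entry is 6/13, or about 46% of it. The formula assumes equal correct-guess rates in both arms and no undecided subjects. It describes bias from a broken blind, which arises whether or not subjects speak. It does not measure the effect of the 6.3 sentence.

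**The case against.** The strongest reply is that the sentence is narrow. It discourages rather than forbids, and it covers only an expected, fading tingle. Pain, twitching and skin reactions are not mentioned. Adverse events are asked about at each visit and all are documented, and changes in health must be reported. Comfort is set by individual adjustment in the lab (Section 2.3.1), and nothing says that the instruction applies during fitting. This largely stands. A reader might infer that the plan suppresses side-effect reports, and the documents do not support that. What remains is a risk created by a missing exception, because the visit inquiry still relies on the same subject's answer.

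A reader might also infer that the instruction removes the only information on whether the blind held. That does not follow either. Unblinding must be reported to the principal investigator, chance remarks to blinded staff would not be systematic data, and the sentence does not prevent a questionnaire. The missing blinding assessment is a separate gap, which the sentence does not cause.

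It is also fair to say that guess data cannot isolate expectation. Guesses partly reflect benefit, and analysis by guess conditions on something observed after randomization. That limits how the data may be used. It is not a reason to leave them uncollected.

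Finally, if the sham delivers equal electrical levels, the blind may be sound. The form would then give the sponsor evidence of it.

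**Conclusion.** The point holds as two linked gaps and should be corrected. Section 6.3 leaves the limits of its instruction unstated, which risks under-reporting of electrode-site effects. The plan also has no systematic way to assess a blind that it concedes may be imperfect, in a crossover whose primary endpoints are all rated or adjusted by the subject.

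The extent of any under-reporting cannot be estimated from the documents. The 1 to 6 TFI points for p between 0.6 and 0.8 are illustrative, since both inputs are assumed. They show that a partly broken blind could matter against the 13-point benchmark. They do not show that it will, and they should not be read as an expected bias.

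Whether sensation reveals the arm, and whether under-reporting could differ by arm, depends on which sham description applies. The documents do not settle that.

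**What to change.** 1. Replace the sentence in Section 6.3 with wording such as: *Subjects are asked not to discuss stimulus sensation with the person administering the TFI, THI or TinnTester. This never limits the reporting of discomfort or of any adverse event, which may be reported at any time.*

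2. Reconcile the sham descriptions in Sections 4.2, 6.3 and 8.2.

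3. Add to Section 1.3 a short self-completed form, hidden from outcome assessors, early in each treatment period (for example at the end of its first week) and at its end. It needs a local-sensation item and a treatment guess (active, sham, don't know) with the reason for the guess (sensation, benefit, other).

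4. Add to Section 9 a blinding index, such as Bang's, reported descriptively by arm and period. Label any analysis of the primary contrast by guess as supportive only. The early guess and the stated reason help to separate sensation from benefit but do not do so fully.

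The cost is one revised sentence, a few questions at visits that already take place, a short paragraph in Section 9 and the usual IRB approval of an amendment. No stimulus level changes. The downside is that asking for a guess may draw some attention to allocation. The form should start as soon as possible, because beliefs not recorded before unblinding cannot be reliably recovered afterwards.
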